Non-invasive Measurement of Blood Glucose,
Blood Pressure and Extrapolation of QRS
Complex Using a Wrist Wearable
Photoplethysmography Sensor

NCT05904769

10November2022

IRB Minimal Risk Protocol Template

Note: If this study establishes a human specimen repository (biobank) for research purposes, do not use this template. Use the Mayo Clinic Human Specimen Repository Protocol Template found on the IRB home page under Forms and Procedures at

[REDACTED]

First-time Use: Use this template to describe your study for a new IRB submission.

1. Complete the questions that apply to your study.
2. Save an electronic copy of this protocol for future revisions.
3. When completing your IRBe application, you will be asked to upload this document to the protocol section.

Modification: To modify this document after your study has been approved:

1. Open your study in IRBe. Click on the study 'Documents' tab and select the most recent version of the protocol. Save it to your files.
2. Open the saved document and activate "Track Changes".
3. Revise the protocol template to reflect the modification points, save the template to your files
4. Create an IRBe Modification for the study and upload the revised protocol template.

General Study Information

Principal Investigator: [name], MBBS, FACC, FHRSC

Study Title: Non-invasive measurement of blood glucose, blood pressure and extrapolation of QRS complex using a wrist wearable photoplethysmography sensor

Protocol version number and date: V1, November 10, 2022

Research Question and Aims

Hypothesis: A non-invasive wrist-based photoplethysmography (PPG) sensor may detect changes in blood glucose level and blood pressure. The PPG signal may also be used to extrapolate a waveform that may be used as a surrogate for the cardiac QRS complex.

Aims, purpose, or objectives:

1. Measure systolic and diastolic blood pressure detected by a wrist-based sensor and compare against standard of care noninvasive cuff blood pressure measurements and/or invasive arterial line measurements.
2. Extrapolate a surrogate waveform for the cardiac QRS complex by training and validating against the reference electrocardiograph (ECG) waveform.
3. Measure blood glucose levels detected by a wrist-based sensor and compare against fingerstick data obtained four times daily in hospitalized diabetic patients
4. Measure blood glucose levels detected by a wrist-based sensor and compare against whole blood glucose identified in hospitalized patients undergoing anticipated blood glucose measurements

Background (Include relevant experience, gaps in current knowledge, preliminary data, etc.): Diabetics on insulin or several oral agents need to monitor blood sugar several times daily. However, checking blood sugar is invasive, requiring at minimum finger stick monitoring, and thus may be prone to issues with compliance. Recent data has suggested that spectral signatures that may be obtained using specific light frequencies over superficial vessels may allow for noninvasive measurement of blood glucose levels, including changes in levels over time. This may allow for non-invasive measurement of blood glucose that may permit pre-diabetic and diabetics to improve continuous and intermittent approaches to monitoring.

Additionally, we are at a paradigm shift in medicine where we are moving away from the traditional 6-monthly or annual follow-ups and entering an era of continuous monitoring. The novel wrist-based photoplethysmography (PPG) sensor would be able to measure systolic and diastolic blood pressure noninvasively and without the sensation of manual pressure. Thus, we can acquire many more data points on patients and potentially detect disease exacerbations before it is too late.

Study Design and Methods

Methods: *Describe in lay terms, completely detailing the research activities that will be conducted by Mayo Clinic staff under this protocol.*

Patients will be asked to wear a wrist-based PPG sensor (LifePlus, Inc) that will be worn throughout their hospitalization. They will be identified on the basis of being diabetic with anticipated four times daily blood glucose checks to be done as part of their regular inpatient care. Data collected will include patient demographics, body mass index, and Fitzpatrick skin tones. Timing of fingerstick checks as well as labs in which whole blood glucose measurements are obtained will be recorded and synchronized against evaluations recorded by the wrist-based sensor. These will then be compared offline for accuracy. Similar comparisons will be made for blood pressure readings and compared to standard vital sign checks on the floor.

For blood pressure measurements, we will additionally study patients who undergo electrophysiologic procedures. We will compare readings on the wrist-based sensor to invasive arterial line measurements and/or noninvasive blood pressure readings obtained via a cuff-inflation in studies such as the tilt-table test. We typically monitor the electrocardiograph (ECG) waveform on these patients as well. During this study, we will collect continuous, time-synced PPG, blood pressure and ECG data from these patients for the duration of the procedure.

Subject Information

Target accrual is the proposed total number of subjects to be included in this study at Mayo Clinic. A "Subject" may include medical records, images, or specimens generated at Mayo Clinic and/or received from external sources.

Target accrual: 200 patients (100 patients hospitalized, and 100 patients undergoing EP procedures)

Subject population (children, adults, groups): adults

**Inclusion Criteria:**

1. Diabetic patients on insulin undergoing four times daily blood sugar checks as part of standard of care.
2. Patients undergoing continuous monitoring for heart rate, ECG and blood pressure as part of their routine care.
3. Patients undergoing invasive and noninvasive electrophysiologic procedures.

Exclusion Criteria:

1. Patients unable to provide informed consent
2. Patients without arms as these are needed to wear the wrist-based sensor

Data Analysis

Power analyses may not be appropriate if this is a feasibility or pilot study, but end-point analysis plans are always appropriate even if only exploratory. Provide all information requested below or provide justification if not including all of the information.

Power Statement: This is a pilot study and thus is not specifically powered to reach a hard outcome. After this exploratory analysis, we will use this to appropriately power a larger study.

Data Analysis Plan: The data will be acquired with direct synchronization between glucose levels obtained by fingerstick or whole blood measurements and blood pressure (manually and invasive arterial line), ECG waveform and from the wrist-based PPG sensor. We will then compare the change in glucose level and blood pressure between measurements estimated by the sensor and by the standard glucose measurements. We will compare the changes in parameters between measurement time points using the standard measurements versus the wrist-based sensor using standard statistical methods (paired student t-test or Wilcoxon Signed Rank test). We will also evaluate what the absolute differences are between the 2 measurement approaches to determine the clinical significance. For the ECG comparison study, we plan to extrapolate a surrogate waveform from PPG and validate it against the reference QRS complex from the ECG waveform.

Endpoints**Primary:**

- 1) Difference between measurement of systolic and diastolic blood pressure using the wrist-based PPG sensor versus standard cuff-inflation and invasive measurement of blood pressure.
- 2) Difference between a surrogate waveform extrapolated from wrist-based PPG sensor versus standard QRS complex reported by the ECG sensor.
- 3) Difference between measurement of blood glucose level using the wrist-based PPG sensor versus standard blood-based measurement of blood glucose.

Secondary: N/A

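### The only named test for blood pressure and glucose is run on changes over time, while primary endpoints 1 and 3 are differences in measured value; the step that could answer them has no statistic, interval or method for repeated readings

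*Combined protocol and SAP*

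**What the plan says.** In the Combined protocol and SAP, under Endpoints (Primary), endpoint 1 is "Difference between measurement of systolic and diastolic blood pressure using the wrist-based PPG sensor" against cuff and invasive pressure. Endpoint 3 is "Difference between measurement of blood glucose level using the wrist-based PPG sensor versus standard blood-based measurement of blood glucose". Both are comparisons of measured values, as are aims 1, 3 and 4. Study Design and Methods says of the synchronized glucose readings: "These will then be compared offline for accuracy". For pressure it adds: "Similar comparisons will be made for blood pressure readings and compared to standard vital sign checks on the floor".

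The Data Analysis Plan names one inferential method for these quantities. What is to be tested is given as follows: "We will compare the changes in parameters between measurement time points using the standard measurements". The same sentence goes on to name the comparator and the test: "versus the wrist-based sensor using standard statistical methods (paired student t-test or Wilcoxon Signed Rank test". It gives no rule for choosing between the two tests. It then adds: "We will also evaluate what the absolute differences are between the 2 measurement approaches to determine the clinical significance". No summary statistic, interval or threshold is attached to that sentence.

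Readings repeat within a patient: fingersticks are taken four times daily and procedure data are recorded continuously. Nothing is said about how repeated pairs enter the analysis. Target accrual is 100 hospitalized patients and 100 undergoing electrophysiology procedures.

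**The concern.** The named test concerns a different quantity from the endpoints. Three consequences follow.

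- A constant error in the sensor cancels when successive readings are subtracted, so the test cannot see it.
- A paired test weighs the mean (or median) error in change against its spread. A noisier sensor is therefore harder to reject, and the spread of individual errors is never reported as a result.
- Even for changes, the test does not show tracking. If the sensor follows the reference one-for-one, the reference trend cancels. If it follows partly or not at all, the result depends on how large the average trend happens to be.

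At stake are the two quantities that endpoints 1 and 3 call for: the bias in level and the spread of individual errors. The Power Statement needs them too: "After this exploratory analysis, we will use this to appropriately power a larger study". A later study cannot be sized from a test on changes, or from an SD and interval that ignore clustering.

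**Working it through.** The plan states no power, alpha or SD, so there is no figure to reproduce. From the documents come the 100 patients per cohort, the named tests and the repeated readings. All other inputs below are assumptions: two-sided alpha 0.05, one independent pair of changes per patient, and SD of reference change 50 mg/dL or 15 mmHg.

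**1. Constant bias.** Write sensor = reference + b + e. The difference in change is (S2 − S1) − (R2 − R1) = e2 − e1, so b is gone. Simulated rejection with level-error SD 8 and n = 100:

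| Offset b | Test on changes | Test on levels |
|---|---|---|
| 15 | 5.0% | 100% |
| 50 | 5.2% | 100% |

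**2. Scatter.** With zero bias, the test on changes rejects 4.7% at level-error SD 8 and 4.9% at SD 30. The 95% limits of agreement in level are 1.96 × 8 = ±15.7 and 1.96 × 30 = ±58.8.

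**3. Tracking of changes.** Let sensor change = k × reference change + error. The mean difference is (k − 1) × mean change, with SD √[((k − 1) × 50)² + error SD²]. Power comes from a noncentral t with 99 df and noncentrality mean/(SD/√100). For k = 0.5 and error SD 8, SD = √(25² + 8²) = 26.2. For a sensor independent of the reference but equally variable, SD = 50√2 = 70.7 and the mean difference equals the mean reference change in size.

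| Glucose sensor | Mean change 0 | 10 | 15 | 25 mg/dL |
|---|---|---|---|---|
| Follows one-for-one, no mean error | 5% | 5% | 5% | 5% |
| Follows half | 5% | 47% | 81% | 99.7% |
| Independent of reference | 5% | 29% | 56% | 94% |

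A one-for-one sensor with a 1 mg/dL mean error in change is rejected 91%, 51%, 24% and 10% of the time at error SD 3, 5, 8 and 15. So the independent sensor at mean change 10 (29%) and this tracking sensor at error SD 8 (24%) look alike. Their 95% limits in change, around the mean error, are 1.96 × 70.7 = ±139 and 1.96 × 8 = ±16 mg/dL.

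For blood pressure, the independent sensor (SD 15√2 = 21.2 mmHg) is rejected 5%, 29%, 65% and 96% at mean changes 0, 3, 5 and 8 mmHg. Wilcoxon simulations of the independent-sensor and 1 mg/dL cases agreed within about 2.5 percentage points.

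**4. Repeated pairs treated as independent.** Take 100 patients with 12 pairs each. The design effect is 1 + 11 × ICC, where ICC is the within-patient correlation of the differences: 3.2 at 0.2 and 9.8 at 0.8. In units of the SD of differences:

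- The correct half-width for bias is 1.96√(3.2/1200) = 0.10 to 1.96√(9.8/1200) = 0.18. Treating pairs as independent gives 1.96/√1200 = 0.06, with true coverage 72% to 46% instead of 95%.
- The correct half-width for each limit of agreement is 0.14 to 0.28 (simulation). Independent pairs would show 0.10, with coverage 83% to 50%.
- A bootstrap by patient covered 93% to 95% (bias) and 92% to 95% (limits) in the cases simulated. These included 60 readings per patient with serial correlation 0.9, where independent-pairs intervals covered 29% and 33%.

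**The case against.** The best defence is that the level comparison is already planned. Synchronized pairs are to be compared for accuracy and absolute differences evaluated for clinical significance, so only detail is missing. That is partly right, and the step deserves credit. But it carries no statistic or interval. If absolute means unsigned, it would give the size of error without the direction of bias. Meanwhile the one method that is specified answers another question.

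Second, the hypothesis is about detecting changes, so a change analysis has a purpose. True, and it should be kept; it still does not answer endpoints 1 and 3. An earlier sentence in the Data Analysis Plan is loose enough to be read as a between-device difference, but the sentence naming the test refers to time points.

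Third, the plan nowhere says that a non-significant result means agreement, so most of the rejection rates illustrate a misreading it does not make. That stands. The offset result is the one that bears directly on the mismatch; the others show why the misreading should be ruled out.

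Fourth, this is an exploratory pilot. That excuses the absence of power, but the instruction at the head of the Data Analysis section expects an endpoint analysis plan even then.

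Finally, precision worsens when results are split by reference method. With an assumed 30 patients, 12 pairs each and ICC 0.8, the half-widths are about 0.31 SD for bias and 0.47 to 0.48 SD for a limit, and bootstrap coverage of the limits is about 88% to 89%. This qualifies the cost, not the finding.

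**Conclusion.** The concern holds, on the text alone: the named test addresses changes, endpoints 1 and 3 address measured values, and the step aimed at measured values is unspecified. That a constant bias cancels is algebra and needs no assumption. The sizes (5% against 100% rejection for an offset; 5% for full, half and no tracking at zero mean change; interval coverage as low as 46% for bias) rest on assumed SDs, correlations and readings per patient. They are illustrations, not predictions for this trial. The plan should be corrected before analysis; the data to be collected can answer both endpoints once it says how.

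**What to change.** In the Data Analysis Plan:

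- Make the absolute-difference step the main analysis of endpoints 1 and 3, defined as signed sensor-minus-reference differences on paired levels.
- Report systolic pressure, diastolic pressure and glucose separately, and by reference method (cuff, arterial line; fingerstick, whole blood).
- For each, give the bias with 95% CI, the SD of paired differences, and Bland-Altman 95% limits of agreement with CIs. Check whether the spread varies with level before using limits of constant width.
- Obtain intervals by bootstrap over patients, or from a mixed model with a patient effect plus serial correlation for the continuous procedure data. State the number of patients and pairs in each analysis, and read intervals from small reference-method groups with caution.
- Keep changes between time points as a secondary analysis, reported the same way.
- State that a non-significant paired test is not evidence of agreement.
- Optionally, add mean absolute relative difference for glucose and acceptance limits written in advance.

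The cost is plan wording and a modest amount of analysis, with no new patients or data. Intervals will be wider than if every pair counted as independent, and wider again in small reference-method groups.

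### The paired tests are named without saying what one pair is or how repeated readings from a patient are handled; if readings or intervals are pooled the error bars are wrong, in a direction that depends on how change is defined

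*Combined protocol and SAP*

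**What the plan says.** The Data Analysis Plan gives one inferential method. It says "We will compare the changes in parameters between measurement time points", with the reference measurements set "versus the wrist-based sensor using standard statistical methods (paired student t-test or Wilcoxon Signed Rank test"). It adds that absolute differences between the two approaches will be looked at for clinical significance, and names no test or confidence interval for them.

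The blood pressure and glucose primary endpoints are differences in level between sensor and reference, not differences in change.

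Study Design and Methods makes repeated readings part of the design:
- The sensor is one "that will be worn throughout their hospitalization", in patients with "anticipated four times daily blood glucose checks to be done as part of their regular inpatient care".
- The times of fingerstick checks and laboratory glucose draws "will be recorded and synchronized against evaluations recorded by the wrist-based sensor".
- On the ward, "Similar comparisons will be made for blood pressure readings and compared to standard vital sign checks on the floor".
- In the electrophysiology (EP) cohort, "we will collect continuous, time-synced PPG, blood pressure and ECG data from these patients for the duration of the procedure".

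Target accrual is 100 hospitalised and 100 EP patients. The Power Statement calls the study a pilot whose results will be used to power a larger one. Nowhere does the document define the pair or mention a per-patient summary, a patient effect, clustered standard errors or any other handling of within-patient correlation.

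**The concern.** A paired t-test or signed-rank test handles the link between the two members of a pair. It does not handle links among several pairs from the same patient. Whether the named tests are valid therefore depends on a choice that the plan leaves open: what counts as one pair.

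Three things are at stake if readings or intervals are pooled:
1. The reported precision would be wrong, for changes and for any interval put on level bias.
2. Patients with long stays would weigh more than patients with short stays, even in a purely descriptive mean difference.
3. A planner of the larger study who counted pairs as if they were patients would recruit too few patients.

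**Working it through.** The documents give no alpha, SD, length of stay or correlation, so there is no stated figure to reproduce.

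**Inputs.** From the documents: n = 100 hospitalised patients and four glucose checks a day. Assumed: stays of 1, 3 or 5 days, so K = 4, 12 or 20 readings and m = K − 1 changes per patient; two-sided alpha 0.05; equal K across patients; no sensor drift. Each sensor-minus-reference difference is a patient effect plus an error with variance σ². Errors are independent at first (lag-1 autocorrelation r = 0). Results use normal approximations for the t-test. The signed-rank test makes the same independence assumption but was not calculated.

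**Successive changes, pooled.** One change has variance 2σ², so the naive variance of a patient's mean change is 2σ²/m. In truth the changes telescope to (last − first)/m, with variance 2σ²/m². Hence naive SE / true SE = √m:
- √3 = 1.73, √11 = 3.32, √19 = 4.36.
- For a bias in change that a per-patient test detects with 80% power, the pooled test has power 1 − Φ(1.96√m − 2.80). At K = 4 this is 1 − Φ(0.59) = 28%; at K = 12 and K = 20 it is about 0.01% or less.

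**Changes from the first reading, pooled.** These share the first reading's error, so any two have correlation σ²/(2σ²) = 0.5. The variance is inflated by 1 + 0.5(m − 1) = 2, 6, 10. Hence:
- naive SE / true SE = 1/√2, 1/√6, 1/√10 = 0.71, 0.41, 0.32.
- type I error = 2[1 − Φ(1.96 × ratio)] = 17%, 42%, 54%.

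**Sensitivity.** With r = 0.8 the ratios are 1.11, 1.55, 1.96 for successive changes and 0.66, 0.38, 0.30 for changes from the first reading. Each error keeps its direction. Drift that differs between patients can reverse the successive-change result. At r = 0, with total SD 1 and intraclass correlation (ICC, the between-patient share of variance) 0.3, the reversal occurs above a drift SD per interval of √(2 × 0.7/m) = 0.68, 0.36, 0.27.

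**Levels, if a pooled CI is reported.** The design effect is 1 + (K − 1) × ICC, and coverage is 2Φ(1.96/√design effect) − 1.

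| K | ICC | Design effect | Coverage of a nominal 95% CI |
|---|---|---|---|
| 4 | 0.1 | 1.3 | 91% |
| 12 | 0.3 | 4.3 | 66% |
| 20 | 0.5 | 10.5 | 45% |

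At ICC 0 coverage is 95%.

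**Weighting.** A 5-day stay gives 5 × 4 = 20 readings and a 1-day stay gives 4, so pooling weights the first patient five times as much.

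**Sizing example.** Assume a target CI half-width of 0.1 SD and 12 readings each. Counting pairs: (1.96/0.1)² = 384.2 pairs, and 384.2/12 rounds up to 33 patients. Allowing for clustering, patients = 384.2 × [ICC + (1 − ICC)/12] = 68, 138, 209 at ICC 0.1, 0.3, 0.5.

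**Check by simulation.** With one summary per patient, type I error stayed at about 5% in every simulated scenario (4.1% to 5.3% for mean change, 4.3% to 5.5% for mean level; 3,000 runs each, ICC 0.5).

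The EP cohort is not quantified, because the documents do not give the number of readings per procedure.

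**The case against.** The plan never says that readings will be pooled. One change summary per patient, or a separate test of each interval across patients, fits the text and is valid. The study is an exploratory pilot with no alpha and no decision rule. For level differences no test or interval is named, so the coverage figures describe an analysis that may never be done. Undersizing the next study needs a planner who counts pairs, and the Power Statement does not say that. Length of stay, ICC, autocorrelation and drift are all assumed.

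All of this stands, and it limits the point to an omission with conditional consequences. It does not remove the omission. The template text under Data Analysis excuses a pilot from the power analysis but says that "end-point analysis plans are always appropriate even if only exploratory", and no justification is given for leaving the unit of analysis out.

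A reader might infer that clustering must make the pooled tests give false positives. The text does not support that: for successive changes without drift the pooled SE is too large. A reader might equally infer that pooled tests on change are conservative unless the sensor drifts differently between patients. That fails too: changes from a first or baseline reading fit the wording just as well, and they give an SE far too small with no drift at all.

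**Conclusion.** The omission is certain: the only named inference assumes independent pairs, the design yields many pairs per patient, and the plan neither defines the pair nor handles within-patient correlation. The harm is conditional on pooling and has no single direction. Pooled successive changes can hide a real bias in change, pooled changes from the first reading can produce a spurious one, and a pooled interval on level bias is too narrow unless the ICC is 0. The sizes rest wholly on the assumed inputs and show what could happen, not what will.

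A reader should not conclude that the planned analysis is invalid or that a trial decision is in danger; the documents support neither. Because the estimates feed a larger study and the remedy is cheap, this should be fixed before analysis.

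**What to change.** Add a few sentences to the Data Analysis Plan:
- Make the patient the unit of inference.
- For systolic pressure, diastolic pressure and glucose separately, analyse sensor-minus-reference level differences with a random patient effect, per-patient summaries or a patient-level bootstrap. Report bias with CIs from that analysis.
- Define the change, as successive or from baseline. Use patient-clustered standard errors, or the named paired test on one change summary per patient. If each interval is to be tested separately, say so and give the number of tests.
- Report the numbers of patients and of pairs, and the between- and within-patient SD, so that the larger study can be sized for its own reading schedule.

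This needs standard software and no new data. The cost is a little more analysis work and wider CIs on level bias than pooling would show.

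### The only inference named for blood pressure and glucose tests for zero mean difference in change, so its p-value cannot show that the sensor is accurate

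*Combined protocol and SAP*

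**What the plan says.** The Methods text under Study Design and Methods gives the purpose of pairing sensor and reference readings: "These will then be compared offline for accuracy". The blood pressure and glucose primary endpoints are sensor-versus-reference differences in measured value; the glucose one reads "Difference between measurement of blood glucose level using the wrist-based PPG sensor versus standard blood-based measurement of blood glucose".

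The Data Analysis Plan then names one inferential procedure. It is applied to how each parameter moves from one reading to the next, with the reference set "versus the wrist-based sensor using standard statistical methods (paired student t-test or Wilcoxon Signed Rank test"). The plan adds one descriptive step: "We will also evaluate what the absolute differences are between the 2 measurement approaches to determine the clinical significance". No summary statistic, confidence interval, limits of agreement or acceptable limit is given for that step.

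The ECG comparison has its own sentence and no named statistic ("we plan to extrapolate a surrogate waveform from PPG and validate it against the reference QRS complex from the ECG waveform"). This point is confined to blood pressure and glucose.

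Target accrual is 100 hospitalized patients and 100 having electrophysiology procedures, with no split by reference method. The Power Statement calls the study an unpowered pilot whose results will be used to power a larger one.

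**The concern.** A paired t-test or signed rank test asks whether the average (or typical) paired difference is zero. Accuracy is a different question: how far sensor readings lie from the reference, on average and individually. Failing to reject zero can mean that the mean error is small, that the errors are too scattered to show it, or that there were too few patients. The p-value does not tell these apart.

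Because the test is on changes, a constant sensor offset also drops out before testing.

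At stake is how the pilot is read. A sensor with wide scatter, or a comparison on few patients, could be reported as not significantly different from the reference and taken as support for accuracy. The p-value also does not supply the bias, scatter and precision needed to design the larger study.

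**Working it through.** **Plan's own figure.** There is none to reproduce. The documents give no alpha, SD, effect size, margin or power.

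**Inputs.** From the documents: the two named tests, their application to changes, and 100 patients per cohort. Assumed: two-sided alpha 0.05; one independent, normally distributed value per patient of d = (sensor change − reference change); true mean of d = 5 mmHg; SD of d from 8 to 40; and n = 20 as an example of a smaller comparison.

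**Formula.** The paired t statistic is non-central t with n − 1 degrees of freedom and non-centrality λ = (5/SD) × √n. The chance of non-significance is P(−c < T < c), where c is the two-sided 5% critical value: 1.984 at n = 100 and 2.093 at n = 20.

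| n | SD of d | λ | Chance of non-significance |
|---|---|---|---|
| 100 | 8 | 6.25 | <0.1% |
| 100 | 15 | 3.33 | 9% |
| 100 | 20 | 2.50 | 30% |
| 100 | 40 | 1.25 | 76% |
| 20 | 8 | 2.80 | 24% |
| 20 | 20 | 1.12 | 81% |

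Simulated Wilcoxon tests at n = 100 gave 0% at SD 8, 11% at SD 15 and 77% at SD 40, so the choice between the two tests does not matter here.

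**Mean error in change of zero.** Then λ = 0 and the chance is 1 − 0.05 = 95% at every SD and every n. Simulating change scores (n = 100, no average shift in the reference) bears this out:
- sensor noise SD 8 or 25 per reading, no offset: 95% non-significant in both cases;
- the same with a constant 20-unit offset: 95% in both cases;
- a flat sensor that ignores the patient: 95%.

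**What scatter-based summaries show.** With mean error 5 and normal errors:
- The half-width of the 95% limits of agreement is 1.96 × SD: 15.7 at SD 8, 29.4 at SD 15, 39.2 at SD 20 and 78.4 at SD 40.
- The mean absolute difference is SD × √(2/π) × exp(−25/(2 SD²)) + 5 × [1 − 2Φ(−5/SD)]: 7.6 at SD 8 and 32 at SD 40.

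Both worsen with noise, while the chance of non-significance at n = 100 rises from <0.1% to 76%.

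**The case against.** **It is an exploratory pilot, and no passage says a p-value will decide anything.** This stands in part. A reader might infer that the plan will declare agreement when p exceeds 0.05. The documents do not support that, because they give no interpretation of the p-value. The misreading is a risk left open, not a planned rule. Pilot status excuses the missing power calculation. It does not make a test of zero difference informative about accuracy, and the protocol template asks for endpoint analysis plans even when exploratory.

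**The plan also looks at absolute differences.** This stands in part. If the phrase means the size of sensor minus reference, a noisy sensor would show up in the report. What is missing is a limit set beforehand, so clinical significance would be judged after the data are seen.

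**The noise effect is conditional.** This stands. It is tempting to say that a noisier sensor is always more likely to pass. That holds only when the mean error in change is not zero. A fixed offset does not produce such an error, and the documents give no basis for its size.

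**Trivial differences becoming significant.** A reader might add that a good sensor would be declared different: a 1 mmHg difference at SD 10 over 2,000 readings is significant 99% of the time. That treats pooled readings as independent, which the plan does not say it will do. With one value from each of 100 patients the figure is 17%, so this is not part of the point.

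**A small arterial-line group.** The protocol gives no split by reference method, so n = 20 is only an example.

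**Conclusion.** The point holds in this form: for blood pressure and glucose, the one named inference tests for zero mean difference in change and cannot show accuracy against the reference. With a mean error in change of 5 mmHg, non-significance has a chance of 9% at SD 15 and 76% at SD 40 with 100 patients, and of 24% at SD 8 and 81% at SD 20 with 20 patients. With a mean error of zero it is about 95% whatever the scatter. The percentages rest on the assumed error, SDs, one value per patient and 5% level. The direction does not: for any non-zero mean error, non-significance becomes more likely as SD rises or n falls.

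The documents do not support the stronger conclusion that the study is set up to pass a poor sensor. Nor does the point require a pass/fail equivalence test, which is debatable in a declared pilot and ignores scatter. At n = 100 with an illustrative 5 mmHg margin, an unbiased sensor with SD 15 passes about 90% of the time, though only 26% of its readings lie within 5 mmHg. The change should be made before analysis.

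**What to change.** In the Data Analysis Plan, drop the t-test/Wilcoxon p-value as the result. For each parameter and each reference method (cuff, arterial line, fingerstick, whole blood), report:

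1. the mean sensor-minus-reference difference, for level and for change, with a confidence interval;
2. the 95% limits of agreement, with confidence intervals around each limit.

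Both should come from an analysis that accounts for repeated readings within patient. The investigators should fix acceptable limits before sensor and reference data are linked, and judge clinical significance against them. The plan should state that neither a non-significant difference nor an interval crossing those limits is evidence of agreement.

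The cost is analysis-plan wording and one decision on limits; recruitment, procedures and data collection do not change. The downside is that small or noisy comparisons will be reported as inconclusive. For example, at SD 15 the 95% interval around each limit of agreement is about ±5.1 units with 100 patients and ±10.7 with 25, from t × SD × √(1/n + 1.96²/(2(n − 1))), where t is the two-sided 5% critical value on n − 1 degrees of freedom.
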